#### **SECTION D. Multi-site Monitoring and Compliance**

This is not a multi-site study.

**SECTION E. Assessment of External Factors**

The PI will conduct a semiannual assessment of external factors through a review of literature related to new developments in the areas of self-management, symptom management (including pain and fatigue), symptom reporting and other approaches that may have an impact on the safety of participants or on the ethics of the study. To determine whether any changes are necessitated to the study protocol, the PI, the mentor, and the members of the SMC will review any identified literature or product safety data that may pose as a potential impact to the risk benefit ratio study and/or safety of study participants.

**SECTION F. Interim Analysis**

This study aims to test the feasibility of a multi-component, technology-based intervention to promote self-management and symptom management among adolescents with sickle cell disease during the transition process from pediatric to adult care and parent-managed to adolescent self-managed care. To our knowledge, there are no similar interventions specifically designed for this patient population and purpose. As such, the BS will generate semi-annual qualitative interim analysis reports on a) adverse events; and b) data obtained during phone call and returned end-of-study surveys to understand issues related to the uptake, usability, and adoption of this platform among this population. We will evaluate the screening and enrollment procedures, barriers to participation and retention, including, safety, adherence, acceptability, technology problems encountered, if any, and user feedback from the participants and providers. This information gained from this structured process will be used to both guide the refinement of the current protocol and to inform the design of a larger efficacy trial. Interim analysis of outcome variables (transition readiness, adolescent pain, adolescent and caregiver fatigue and other symptoms, and quality of life) was not considered to avoid inexact inferences and increased chance of error due to few data points, as well as potential for bias if interim results were known to the investigators. Therefore, there are no planned stopping rules for this study.

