Data on young adult-provider or dyad-provider communication and healthcare activities will be collected via MyChart messaging. All messages between young adults and providers or dyads and providers will be retrieved as transcripts for analysis. Patients and families at the MUSC Pediatric Sickle Cell clinic do not frequently use MyChart messaging to communicate with providers and instead send text messages. To encourage use of the more secure EHR portal (MyChart) – which has the added benefit of improved provider workflow – participants will be compensated for sending messages via MyChart. Participants will be compensated with \$2 for each message with a maximum possible compensation of \$20. The number of messages sent will be tallied at the end-of-intervention (12 weeks) and provided in the form of a gift card at that time.

Data on self-management behaviors, including monitoring and tracking symptoms and administering home medications and treatments will be collected via the app and stored in the secure app database. Specifically, we will collect data on the frequency symptoms are recorded (pain, fatigue, fever, etc.) and the frequency of accessing the pain graph component of the app. We will also collect data via the app on medication adherence and recorded treatments for symptoms (drinking water, heating pad, etc.). Data on clinic appointment attendance, ED visits, and details of appointments to assess acceptability of the intervention will be obtained during weekly phone checks. Also during weekly phone checks, adolescent participants will be asked 2 – 3 questions on functioning from the PedsQL Sickle Cell Disease Module and young adult participants will be asked 2 – 3 questions on functioning from the Adult Sickle Cell Quality of Life Measurement Information System (ASCQ-Me).

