Reach: (primary aim) Sample Recruitment	Electronic log of sample characteristics; recruitment and enrollment activities	Recruitment tracking tools	Ongoing
Efficacy: Self-management outcomes (primary aim): Monitoring and tracking symptoms Attending clinic appointments Administering home medications and treatments Symptoms and health-related outcomes (secondary aim): Healthcare utilization (A only) Transition Readiness (A only) Pain (A only) Fatigue (A/CG) Depression (A/CG) Anxiety (A/CG) Sleep Interference (A/CG) Self-Efficacy (A/CG) Quality of Life (A/CG)	Pain and other symptom recording; treatments recorded; utilization reports 
 
PROMIS Pain Interference : Adult/Peds/parent proxy (8;0.87) (26)
 
PROMIS Fatigue SF : Adult (4; >0.9)(27); Peds/parent proxy (10 ; 0.87)(28)
 
PROMIS Emotional Distress: Depressive Symptoms SF : Adult (4; 0.97) (29); Peds/parent proxy (8; 0.94)(30)
 
PROMIS Emotional Distress: Anxiety SF Adult (4;0.97) (31); Peds/parent proxy (8; 0.83) (26)
 
PROMIS Self-Efficacy including general, manage daily activities, manage meds/treatment, manage symptoms: Adult (16; 0.97) (32)
 
Sickle Cell Self Efficacy Scale (9)
 
PROMIS Sleep Disturbance: Adult (4; 0.88)(33)
 
Adolescent Sleep Wake Scale (28; 0.86) (34)
 
Peds QL with Sickle Cell Disease Module (43; 0.95) (35)
 
Adult Sickle Cell Quality of Life Measurement Information System (30)
 
PROMIS Global Health Adult (10)
 
STARx (18; 0.8) (36)
 
Youth and Parent Sickle Cell Responsibility Scale
 
	YA, A/CG report Web-based application data capture Semi-structured interview Quality checks	Baseline, 6 weeks, 12 weeks, 3-months post intervention Ongoing Weekly
Adoption: (primary aim) Adherence (A/CG, HCP) Acceptability (A/CG, HCP) Education (A/CG) Symptom monitoring and tracking (A/CG) Communication (A/CG, HCP)	App overall use data; app component use data; satisfaction; reported problems; YA, A/CG-provider message content; MAUQ_SPA	Web-based application data capture Semi-structured interview Quality checks	Post intervention Ongoing Weekly

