## 11.0 Data Management

**Sex as a biological variable.** We recruit equal numbers of male and female adolescents and preliminarily explore for differences by sex in outcomes, such as acceptability, satisfaction, communication content, symptoms, quality of life, transition readiness, and utilization by conducting preliminary subgroup analyses in preparation for the subsequent larger trial.

**Feasibility processes.** Variables will include those pertaining to study procedures as well as participant variables. Specifically, 95% confidence intervals for proportions will be used to estimate dichotomous outcomes including the proportion of YA, A/CG who agree to participate out of the number approached, the proportion adherent to the intervention protocol, i.e., providing daily symptom monitoring/tracking, using the education component, responding to messaging, lost to follow up, etc. For the continuous feasibility measures (length of time spent in app components), frequency distributions and the median and mean responses with 95% confidence intervals will be obtained. Benchmarks for feasibility success are recruitment rate of at least 2 YA or A/CG per week, retention rates of 70%, use of at least one component of the app  $\geq 2$  days per week (adherence), and expressed satisfaction in key informant interviews (37).

**Outcome measures and estimates of variability.** Secondary aim outcomes variables will include measures of symptoms (pain, fatigue, depression, anxiety, sleep interference), quality of life, transition readiness, and utilization (number of appointments kept, number of ED visits). Demographic and clinical variables obtained at baseline will be described via measures of central tendency (mean, median), variability and frequency distributions as appropriate. Additionally, demographic and clinical characteristics for those who adhered to the study protocol versus those who did not adhere (non-adherers and drop outs) will be compared to better describe the study population. For continuous quality of life measures, the difference between pre-and post-intervention measurements will be estimated via 95% confidence intervals. To assess preliminary intervention effects, we will conduct repeated measures ANCOVA with variables in individual models adjusting for “dose” defined as number of times each portion of the app was accessed, total time spent in each portion of the app, number of days symptoms were recorded, and number of A/CG-provider messages.

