**[name]** will be responsible for the classification of all reported adverse events (AE) and ensuring that all serious adverse events (SAE) are forwarded to the PI, her mentor, and the other members of the SMC within 24 hours and in compliance with MUSC IRB and NINR's reporting requirements. In addition, and in conjunction with the PI, the PC will be responsible for amending the protocol in accordance with SMC recommendations, submitting reportable SAEs to the IRB; and, submitting annual Progress Reports to the NIH/NINR through MUSC's OSRP. The PC will also be responsible for ensuring data management validation and verification of the electronic study research database, and the accurate reporting and timely notification of all AEs to the PI, and the other members of the SMC. As part of the SMC, the PC will be responsible for: conducting monthly internal quality control audits on all participant records and notifying the PI of any deficiencies; participating in data safety monitoring study management meetings; assisting in the generation of ad hoc participant data safety reports as requested; and, the forwarding of reportable SAEs to the NIH/NINR Program Official through MUSC's Office of Research and Special Programs (OSRP) within 72hrs of IRB review and acknowledgement.

**[name]** is the Director of Research at College of Nursing and a member of MUSC Institute of Human Values with Fellowship certification in Research Ethics. [name] has served and is currently serving as a member of numerous NIH/NINR RO1/R21/P20 DSM Boards and Committees, and FDA Industry Sponsored Clinical Trials. Additionally, he also has over 6 years of experience working on HRSA and PCORI funded demonstration programs and studies among patients with Sickle Cell Disease. With no study involvement, [name] has no apparent conflict of interest to serve in this capacity. [name] will be responsible for conducting semi-annual interim analyses, generating semi-annual AE safety reports from the electronic study research database and disseminating de-identified information to the other members of the SMC. The interim data analyses will only include safety related results; analyses in regard to study outcome will not be performed. The interim AE reports will provide typology, frequency data and outcomes of all reported and documented AE in the electronic study database. As part of the SMC, [name] will also participate in safety monitoring study management meetings.

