## **SECTION B. Procedures for Safety, Risk and Confidentiality**

### **1) Monitoring Study Safety**

From the initial screening of the participant by inclusion and exclusion criteria to the informed consent process to the provision of participant study instruction to staff training in Good Clinical Practices (GCP) and regulations pertaining to the Conduct of Human Participant Research to weekly contact with participants to internal monthly quality control audits and protocol fidelity monitoring to the real-time review of AE by the SMC to the oversight of MUSC's IRB, procedures for monitoring study safety are consistently carried out throughout the study. Specific procedures include:

- Participants will be screened for inclusion and exclusion per the protocol; the PI or PC shall verify 100% of participants' eligibility prior to study enrollment through review of inclusion and exclusion criteria with potential participants.
- Participants will be fully informed as to all known risks and the possibility of risk from study participation in the informed consent process. These risks are minimal.
- Participants will be instructed to notify the researchers of any/all suspected or experienced adverse events whether they believe them to be related or not to the intervention.
- The PI or PC will track all reported participant AEs through to resolution. Please see Section C. 1 – 4.
- All investigators and research staff will maintain active CITI training.
- The PI or PC will maintain weekly contact with all participants to elicit information about AEs and to monitor participant study progress, compliance and safety.
- The PI or PC will review participants study logs for fidelity compliance with the intervention.

- The PI or PC will conduct a monthly internal quality control audit of all participant records to ensure compliance with MUSC IRB regulations; the PI and PC will work together to correct any errors.
- The PI and/or designee will observe and evaluate ten (10%) percent of eligibility screening visits, informed consents and study instructions performed by IRB approved study personnel and provide feedback and/or retraining of study personnel if fidelity to both applicable federal regulations and the protocol is not observed.
- The BS shall generate semi-annual AE reports for the PI, mentor, and the SMC to review.
- The SMC will have access to data on SAE within 24 hours and will be able to provide immediate recommendations to the PI, her mentor, and the PC.

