### **SECTION C. Procedures for Identifying, Reviewing and Reporting Adverse Events**

**1) Identifying.** Potential minimum risks identified for participants are outlined in the Protection of Human Subjects section of the K23 grant application and are also outlined in the IRB-approved protocol and informed consent document. Additional unknown risks may occur and, if so, will be identified through diligent monitoring by the PI, mentor, or PC throughout the conduct of this study. During the informed consent process, participants will be advised of the potential risks of participation as identified in the IRB-approved informed consent document and reminded throughout the study that the researchers should be promptly informed about any concerns regarding potential side effects, adverse events, or clinical deterioration. Participants will also be instructed to notify the PI, PC, and/or designee of any suspected adverse events immediately if possible. All participants will be recruited via the MUSC Pediatric Sickle Cell clinic and will be current patients of the clinic. Therefore, if a participant notifies the PI or PC of an acute medical event, the participant will be advised to follow the usual processes of care as directed by his/her regular provider at the Pediatric Sickle Cell clinic. This may include calling the Pediatric Sickle Cell clinic during regular hours, calling the on-call provider after hours, or going to the emergency department if recommended by the regular provider. Throughout the course of study enrollment, the researchers will maintain weekly telephone and/or face-to-face contact with the all study participants to elicit information about experienced AE and to monitor participant progress. The PI or PC will maintain an electronic record of all reported adverse events and notify the SMC of all reportable events as they occur. The SMC will have real-time access to the study database to review and monitor all reported SAE that were reported as related to the intervention. The PI (with the mentor) or PC will generate and provide de-identified monthly administrative human subject safety reports for the SMC to review participant progress, accrual and attrition rates, and monitor the frequency of all reported side effects and AE. Additionally, the BS will generate and provide de-identified cumulative administrative human participant semi-annual safety reports for the SMC to review.

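### Does the semi-annual interim report let study outcomes in, when another section limits it to safety?

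*Combined protocol and SAP*

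**What the plan says.** Four places describe what the biostatistician produces every six months.

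- **Section A.2, Individual Roles and Responsibilities:** "The interim data analyses will only include safety related results; analyses in regard to study outcome will not be performed". The name is removed here. The duties match those given to the biostatistician elsewhere, so that is how the role is read.
- **Section B.1, Monitoring Study Safety:** "The BS shall generate semi-annual AE reports for the PI, mentor, and the SMC to review".
- **Section C.1, Identifying:** "the BS will generate and provide de-identified cumulative administrative human participant semi-annual safety reports for the SMC to review".
- **Section F, Interim Analysis:** "the BS will generate semi-annual qualitative interim analysis reports on a) adverse events; and b) data obtained during phone call and returned end-of-study surveys". The call and survey data are there to show problems with uptake, usability and adoption. The section goes on to a review of enrollment, retention, adherence and acceptability. It then says that interim analysis of outcome variables was not considered, names transition readiness, pain, fatigue and other symptoms, and quality of life, and states that there are no stopping rules.

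Section 10.0 sets out what the calls contain: "Data on clinic appointment attendance, ED visits, and details of appointments to assess acceptability of the intervention will be obtained during weekly phone checks". Each call also carries two or three items for adolescents ("questions on functioning from the PedsQL Sickle Cell Disease Module and young adult participants will be asked" the counterpart items from ASCQ-Me). Section 11.0 defines a secondary outcome as "utilization (number of appointments kept, number of ED visits" and Table 1 lists as primary-aim self-management outcomes "Monitoring and tracking symptoms Attending clinic appointments Administering home medications and treatments".

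**The concern.** One section confines the report to safety and another puts non-safety data into it. The calls that supply those data mix process information (problems, help needed, views of the app) with outcome information (appointments kept, ED visits, functioning items), and no item-level list separates the two. Nor does Section F say whether its end-of-study survey is the one at 12 weeks or the one three months after the intervention.

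Section F itself gives a reason to care: it cites possible bias if investigators learn interim results. Section B.1 sends the biostatistician's adverse-event report to the investigator and mentor, and Section 14.0 says the investigator conducts the key informant interviews. If outcome summaries reached the investigator half-yearly, they could colour later contacts and interviews.

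**Working it through.** The plan gives no figure to reproduce. The check is a comparison of texts, followed by a rough count of the data involved.

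**1. Which sections conflict.** Only Section A.2 uses exclusive wording. Sections B.1 and C.1 call the report an adverse-event or safety report without saying it holds nothing else. A report with an adverse-event part and a process part satisfies B.1, C.1 and F. The literal conflict is A.2 against F.

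**2. Quality of life.** Section F names it among the variables not analysed at interim. The PedsQL and ASCQ-Me call items are quality-of-life items, so they are already barred.

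**3. Utilization and attendance.** Neither is named in Section F's list. Three things still point to exclusion: the list illustrates the general term outcome variables, the call data are wanted for uptake and usability, and A.2 bars analyses of study outcome. Some acute-care events belong in the adverse-event part in any case, since Section C.2 classes inpatient hospitalization as serious.

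**4. Feasibility measures.** Sections 1.0, 4.0 and Table 1 treat enrollment, adoption and acceptability as primary-aim measures. On the widest reading of study outcome, A.2 would forbid the process review that Section F describes. On the natural reading, A.2 means the health and symptom outcomes that F lists, and the two sections agree on what is barred. Only the word limiting the report to safety then remains at odds with F.

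**5. How much data is involved.** Assumptions: 45 units (30 dyads + 15 young adults), unit *i* enrolling at week *i*/*r*, one call per unit per week for *W* weeks, first report at week *T* = 26. The call period is not fixed in one place, so *W* runs from 12 (intervention) to 26 (whole enrollment).

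Calls in hand = Σ max(0, min(*W*, *T* − *i*/*r*)), out of 45 × *W* planned.

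| Rate *r* per week | *W* = 12 | *W* = 26 |
|---|---|---|
| 2 (Section 11.0 benchmark) | 463.5/540 = 85.8% | 652.5/1170 = 55.8% |
| 1 | 234/540 = 43.3% | 325/1170 = 27.8% |

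Surveys due by week 26 at *r* = 2:
- 12-week survey: *i*/2 + 12 ≤ 26, so *i* ≤ 28, giving 28 of 45.
- Three-months-post survey: *i*/2 + 24 ≤ 26 gives 4 if it falls at week 24 of participation, and 0 if it falls at week 26.

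These counts show how much raw material exists at the first report. They do not show that any outcome would be summarised, or that anything would be biased.

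**6. What depends on the report's scope.** Section 11.0 plans confidence intervals for feasibility proportions and means, intervals for pre-to-post differences, and repeated-measures ANCOVA adjusted for app use. None takes the semi-annual report as an input. With no stopping rule there is no interim decision and no error rate to protect, and with one group there is no between-arm difference to reveal.

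**7. What the investigators know anyway.** Under Section B.1 the investigator or coordinator contacts every participant weekly. Section 11.0 puts recruitment and retention on the agenda of team meetings that review a monthly report. Section 14.0 lets study personnel see depression scores immediately.

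**The case for a change.** The strongest opposing case is that two sentences in one protocol cannot both be obeyed, and that the purpose given in Section F does not rescue them: even a process-only report covers primary-aim measures, and its results may be used to refine the protocol while the study runs. Reconciling the wording would cost nothing in data, visits or staff.

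Much of this stands as a matter of drafting. A.2 and F do differ, utilization is missing from F's list, and the survey time point is not given. The step from there to a needed change fails. Either scope would be acceptable, so reconciling the text does not steer the study towards a better design. Section F declares openly that process findings may refine the protocol, which suits a feasibility study, and whichever report carries those findings, that use of them is the same. The bias argument is weak too: Section F names no recipients for the call and survey item, and the people who might be influenced hear the participants' accounts every week.

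**Conclusion.** No change is called for, because there is nothing to gain. The inconsistency comes down to one restrictive sentence in Section A.2 against one item in Section F, plus an incomplete list and an undefined survey label. A biostatistician reading both sections would report adverse events, summarise usability and uptake from the calls, and leave the outcome measures for the final analysis.

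The effect on the estimates planned in Section 11.0 is nil, and no measurable effect on bias, precision, participant safety or the conclusions can be shown. This rests on the single-group design, the absence of stopping rules, the weekly contact by the investigator or coordinator, and the reading of the unnamed role in A.2 as the biostatistician. A comparative design, or interim results that could stop the study, would give the discrepancy real weight.
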